10.4 RECORDING REQUIREMENTS

10.4.1 Severity

The Investigator will provide an assessment of the severity of each AE by recording a severity rating on the AE page of the participant's CRF. *Severity*, which is a description of the intensity of manifestation of the AE, is distinct from *seriousness*, which implies a participant outcome or AE-required treatment measure associated with a threat to life or functionality. Severity will be assessed according to the following scale:

Mild: A type of AE that is usually transient and may require only minimal treatment or

therapeutic intervention. The event does not generally interfere with usual

activities of daily living.

Moderate: A type of AE that is usually alleviated with additional specific therapeutic

intervention. The event interferes with usual activities of daily living, causing discomfort but poses no significant or permanent risk of harm to the research

participant.

Severe: A type of AE that interrupts usual activities of daily living, or significantly affects

clinical status, or may require intensive therapeutic intervention.

10.4.2 Causality

For all AEs, the Investigator must provide an assessment of causal relationship to study drug. The causality assessment must be recorded on the AE page of the participant's CRF. Causal relationship must be assessed according to the following:

• **Related**: An event where there is a reasonable possibility of a causal relationship between the event and the study drug;

• **Unrelated:** Any other event.

10.4.3 Laboratory Abnormalities

All of the following laboratory abnormalities should be captured as AEs:

• Any laboratory test result that meets criteria for an SAE;

• Any laboratory abnormality that resulted in study discontinuation;

- Any laboratory abnormality that required the participant to receive specific corrective therapy;
- Any laboratory abnormality that the Investigator considers to be clinically significant.

Ongoing abnormal laboratory values/conditions that are being treated at baseline will be captured as an AE if the abnormality increases in severity and/or frequency while on study or if the abnormality requires more frequent treatment. If a participant is treated for an abnormal laboratory value just before the Screening Visit, then the medical history should reflect the severity of the abnormality before treatment.

10.5 UNBLINDING

In the scenario that the Investigator must unblind a participant, the Investigator will have access to individual sealed unblinding envelopes, which can be opened to identify the treatment assignment for an individual participant in an emergency. The reason for breaking the blind must be documented in the participant's CRF.

The Investigator, all other study personnel not previously noted, and the participant will remain blinded to the participant's treatment assignment throughout the study.

10.6 TERMINATION OF PARTICIPANTS

Participants will be informed that they have the right to withdraw from the study at any time for any reason, without prejudice to their medical care. The Investigator will make reasonable efforts to keep each participant in the study. However, if the Investigator removes a participant from the study or if the participant declines further participation, the evaluations required at the EOT Visits should be performed if possible. All evaluations and observations, together with the description of the reason(s) for study withdrawal, must be recorded on the appropriate page of the participant's CRF.

The following are justifiable reasons for the Investigator to withdraw a participant from the study:

- The occurrence of an AE;
- Withdrawal of consent;
- Unforeseen events: any event that, based on the Investigator's judgement, makes further treatment inadvisable;
- Serious violation of the study (including persistent participant attendance failure and non-compliance).

An effort must be made to determine why a participant fails to return for the necessary visits or is dropped from the study. Regardless of the reason for termination, all data available for the participant at the time of discontinuation of follow-up should be recorded where applicable on the CRF. All reasons for discontinuation of treatment should be documented.

11. STATISTICAL METHODS

Details regarding the statistical methods will be provided in the Statistical Analysis Plan (SAP), to be finalised before unblinding of the study.

11.1 DETERMINATION OF SAMPLE SIZE

A power calculation was used to determine how many participants will be required, as can be seen below. A total of 40 (20 in each group) participants are required to complete the study, with 120 needed to enter screening to account for ineligible participants and dropouts.

To achieve 80% power to detect a difference of 2.2 cm or more (using a simple 2-sided t-test with estimated SD = 2.4 cm and the conventional 5% significance level) in the mean change in abdominal girth (as measured by AIP AUC) from the start to the end of the day, between the active and placebo groups, 20 participants per group (40 participants in all) are required. Assuming a 15% dropout rate, 47 participants would need to be randomised to yield 40 evaluable participants. Estimating a 60% screen/pretreatment failure rate (mostly from failure to meet abdominal girth criteria, but also pretreatment abdominal pain and abdominal bloating criteria), 120 participants may need to enter screening to achieve 40 randomised participants.

11.2 ANALYSIS POPULATIONS

11.2.1 ITT Population

The Intent-to-treat (ITT) Population will consist of all participants randomised to a treatment group at the Randomisation visit (visit 4).

11.2.2 Safety Population

The Safety Population will consist of all randomised participants who received at least one dose of study drug.

11.2.3 Evaluable Population

The Evaluable Population will consist of all participants included in the Safety population presenting no major protocol deviations with the potential to bias the criteria for evaluation and with full follow-up.

11.3 STATISTICAL ANALYSES

11.3.1 General Considerations

A more detailed description of the statistical methodology will be given in the Statistical Analayis Plan which will be finalised before unblinding of data.

Distribution of study parameters and covariates will be summarised depending on the type of variable with the number of subjects and the number of missing data (where relevant).

Verification of the normality of the distribution for continuous data will be carried out by graphical inspection and consideration of skewness and kurtosis measures.

Descriptive statistics will be presented as;

- Qualitative data: number and percentage of participants in each category
- Ordinal qualitative data: number and percentage of participants in each category, median, interquartiles, range
- Continuous normally distributed data: number, mean, standard deviation, range
- Continuous non-normally distributed data: number, median, interquartiles, range

All statistical comparison tests will be performed using the conventional two-sided significance level of 5%.

11.3.2 Disposition, Demographics, and Baseline Characteristics

The number of screen failures (i.e., participants who entered the Screening Period but not the Pretreatment Period) and the number of pretreatment failures (i.e., participants who entered the Pretreatment Period but were not randomised) will be tabulated by reason for failure.

The overall number of participants screened and the number of participants randomised to each treatment group will be presented. The number and percentage of participants included in each of the analysis populations (ITT, Safety, and Evaluable) will be presented by treatment group and overall. The number and percentage of participants who completed the study or discontinued early, including the reason for discontinuation, will be presented by treatment group and overall.

Participant demographics (age, sex, race, ethnicity, weight, height, and BMI [defined as weight in kg divided by height in meters squared]) and other relevant baseline characteristics will be summarised by treatment group for the ITT Population.

11.3.3 Efficacy Analyses

Assessment of efficacy of treatment will be based on changes between baseline data provided at the Randomisation Visit (Visit 4) and subsequent study visits. Linear interpolation (for the 24 hr recorded girth data) or multiple imputation methods will be used to account for missing outcome data where appropriate . All analyses will be carried out on the ITT, Safety and Evaluable Populations.

11.3.3.1 Primary Efficacy Endpoint

Change from Baseline in Abdominal Girth at Week 4

The mean change from randomisation (Visit 4) to the end of the study (Visit 8) in abdominal girth (as measured by AUC) determined by 24-hour AIP (with hourly averages), between the linaclotide and placebo groups.

The AUC will be calculated using the Trapezoidal method from the first reliable hour of measurement to last measurement (bedtime). The AUC for each patient will then be individually standardised by dividing the total AUC over the period by that patient's number of hours of measurement included in the AUC.

In case of missing data in the middle of the valid period of measurement, AUC is calculated with linear interpolation.

11.3.3.2 Primary Efficacy Analysis

Changes in girth from the first hour of the 24-hour AIP at Visit 8 will be compared between the linaclotide and placebo groups with the AUC measure, adjusting for the corresponding changes in girth at Visit 4 and any other important confounding factors (such as age and BMI), using analyses of covariance.

11.3.3.3 Secondary Efficacy Endpoints

The secondary efficacy endpoints are as follows:

Change from Baseline in Abdominal Distension at Week 2

The mean change from randomisation (Visit 4) to (Visit 6) in abdominal girth (as measured by AUC) determined by 24-hour AIP, between the linaclotide and placebo groups.

Change from Baseline in Maximal Abdominal Distension at Week 4

The maximum change in girth from the first hour, over the period from the 2nd hour to bedtime. The percentage change in maximum distension from baseline to 4 weeks will also be calculated.

Change from Baseline of symptom severity (abdominal pain, discomfort, bloating, and distension)

Daily diary scores for each of the digestive symptoms and a composite score of these parameters will be averaged to obtain 'weekly' scores as follows;

Baseline = mean (day -7 to day -1)

Week 1 = mean (day 1 to day 7)

Week 2 = mean (day 8 to day 14)

Week 3 = mean (day 15 to day 21)

Week 4 = mean (day 22 to day 28)

Change from Baseline in Digestive sensations (subjective bloating, abdominal discomfort, abdominal distension and abdominal pain) at Weeks 4 and 8

The mean change from randomisation (Visit 4) to Visit 6 and from randomisation to Visit 8 in each of the hourly measures of digestive sensations (as measured by AUC), between the linaclotide and placebo groups.

Change from Baseline of Bristol Stool Form Scale at Weeks 4 and 8

Daily diary BSFS scores will be recoded to represent discrepancies from a 'normal' stool type 4 as follows:

- Type 1 coded 3
- Type 2 coded 2
- Type 3 coded 1
- Type 4 coded 0
- Type 5 coded 1
- Type 6 coded 2
- Type 7 coded 3

Hence a higher score represents greater discrepancy from a 'normal' stool consistency.

Daily average recoded BSFS scores for each subject will be computed by averaging over the first 1, 2 or 3 stools as appropriate. For a subject with no stools on a particular day then their BSFS daily average BSS for that day is denoted as 'missing'.

The following means will be calculated for each subject:

- Baseline = mean (day -7 to day -1)
- Week 1 = mean (day 1 to day 7)
- Week 2 = mean (day 8 to day 14)
- Week 3 = mean (day 15 to day 21)
- Week 4 = mean (day 22 to day 28)

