least 6 of the first 12 weeks of the Treatment Period. For the MCP-103-302 trial, 33.7% of linaclotide-treated patients met this primary endpoint, compared with 13.9% of patients who received placebo. Similarly, in the LIN-MD-31 trial, 33.6% of linaclotide-treated patients met this primary endpoint, compared with 21.0% of patients who received placebo (for both trials, p < 0.0001 for linaclotide versus placebo).

Statistically significant improvements were demonstrated in patients' abdominal symptoms (including abdominal pain, discomfort and bloating) and bowel symptoms (including CSBM frequency, spontaneous bowel movement (SBM) frequency, stool consistency and straining). These improvements were sustained throughout 12 weeks of the Treatment Period of each of the two trials and for 26 weeks in Trial MCP-103-302. The results from the RW Period showed that there was no evidence of development of tolerance, nor was there evidence of rebound worsening of bowel or abdominal symptoms relative to baseline once linaclotide was discontinued.

Linaclotide was well tolerated in the IBS-C Phase 3 efficacy trials. Treatment-emergent adverse events (TEAEs) occurred in 54.9% of placebo-treated and 60.8% linaclotide-treated patients. Diarrhoea was the most frequent TEAE and was reported in 3.0% of placebo-treated patients and 19.8% of linaclotide-treated patients. Diarrhoea was generally mild to moderate in severity. Diarrhoea resulted in the discontinuation of 0.4% of patients treated with placebo and 5.3% treated with linaclotide. There were 9 (1.1%) SAEs in placebo-treated patients and 6 (0.7%) in linaclotide-treated patients. The SAEs were judged to be unlikely or unrelated to treatment by the Investigator, with the exception of 2 SAEs (pericarditis and pericardial effusion occurring in 1 patient treated with linaclotide) that were judged by the Investigator to be possibly related to treatment. There were no deaths. One patient died in the Screening Period but never received either linaclotide or placebo. Overall, there was no obvious pattern in the types of SAEs experienced in either the placebo or linaclotide group. There were no SAEs of diarrhoea.

Refer to Section 6 of the United States Package Insert (USPI) for a more detailed description of the safety of linaclotide, as it will serve as the Reference Safety Information for this study. Refer to the Investigator's Brochure for a more detailed description of the IBS-C and CIC clinical

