6.3 EXCLUSION CRITERIA

Participants who meet any of the following criteria will not be eligible to participate in the study:

- 1. Participant reports loose (mushy) or watery stools (BSFS score of 6 or 7) in the absence of any laxative, suppository, enema, or prohibited medicine (as described in Appendix 1) for > 25% of BMs during the 12 weeks before the Screening Visit.
- 2. Participant has ever had a diagnosis of familial adenomatous polyposis, hereditary nonpolyposis colorectal cancer, or any other form of familial colorectal cancer, or inflammatory bowel disease.
- 3. Participant currently has both unexplained and clinically significant alarm symptoms (lower GI bleeding, iron-deficiency anaemia or any unexplained anaemia, or weight loss) or systemic signs of infection or colitis.
- 4. Participant currently has active peptic ulcer disease (i.e., disease that is not adequately treated or stable with therapy).
- 5. Participant has a history of any chronic GI condition (e.g., diverticulitis) that can be associated with abdominal pain or discomfort.
- 6. Participant has CNS disease or any organic condition associated with constipation.
- 7. Participant has had surgery that meets any of the following criteria:
 - a. Has undergone any surgery within 6 months prior to the Screening Visit;
 - b. Has had previous abdominal surgery except appendectomy, cholecystectomy, or hysterectomy.

- 8. Participant has diabetes.
- 9. Participant reports using a Prohibited Medicine (excluding laxatives, suppositories, and enemas) during the Pretreatment Period or is not willing or able to abide by the restrictions regarding use of Prohibited Medicines defined in Appendix 1. (Note: the use of fibre, bulk laxatives, or stool softeners [such as docusate] is acceptable provided that the participant has been on a stable dose during the 30 days before the Screening Visit and plans to continue on a stable dose throughout the study.)
- 10. Participant has taken commercially available linaclotide during the 30 days prior to the Screening Visit.
- 11. Participant is drinking alcohol above the recommended safe alcohol limit (< 21 units/week) or abusing drugs. In addition, participants will be asked to refrain from drinking alcohol for 24 hours before plethysmography recordings until belt removal.
- 12. Participant has lactose intolerance.

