9.1.2 Secondary Efficacy Assessments and Additional Efficacy Assessments Daily Diary

The secondary efficacy assessments are the diary questions that determine the following:

- Daily participant assessment of abdominal pain, discomfort, bloating, and distension;
- Whether a BM is an SBM;
- Whether an SBM is a CSBM;
- Stool consistency (Bristol Stool Form Scale [BSFS]) with each BM.

To determine these secondary outcome measures, participants will be asked to complete paper daily diaries in the evening (or approximately the same time each day) recording:

• Daily Participant Assessment of Bowel Habits:

"Have you taken any laxatives, suppositories, or enemas since yesterday?"

1=Yes

2=No

"If yes, which rescue medicine did you take?"

1=Oral Bisacodyl

2=Bisacodyl suppository

3=Other laxatives, suppositories, or enemas

"How many bowel movements did you have since yesterday?"

"Did you feel like you completely emptied your bowels?"

1=Yes

2=No

"Please refer to the laminated Bristol Stool Form Scale given to you. Please describe the consistency of the bowel movement using the following scale where:"

1=Separate hard lumps like nuts (difficult to pass)

2=Sausage shaped but lumpy

3=Like a sausage but with cracks on surface

4=Like a sausage or snake, smooth and soft

5=Soft blobs with clear-cut edges (passed easily)

6=Fluffy pieces with ragged edges, a mushy stool

7=Watery, no solid pieces (entirely liquid)

Daily Participant Symptom Severity Assessments

"How would you rate your abdominal pain at its worst over the last 24 hours? Enter a number from 0 to 10, where 0 represents no abdominal pain and 10 represents very severe abdominal pain."

"How would you rate your abdominal discomfort at its worst over the last 24 hours? Enter a number from 0 to 10, where 0 represents no abdominal discomfort and 10 represents very severe abdominal discomfort."

"How would you rate your abdominal bloating at its worst over the last 24 hours? Enter a number from 0 to 10, where 0 represents no abdominal bloating and 10 represents very severe abdominal bloating."

"How would you rate your abdominal distension at its worst over the last 24 hours? Enter a number from 0 to 10, where 0 represents no abdominal distension and 10 represents very severe abdominal distension."

Digestive Sensations Questionnaire

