	Abdominal Score: calculated weekly; the daily average of the following individual items (pain, discomfort, bloating) will be calculated, then the weekly average will be calculated as the mean of day 1 to day 7.		
	Abdominal Score plus Distension: calculated weekly; the daily average of the following individual items (pain, discomfort, bloating, distension) will be calculated, then the weekly average will be calculated as the mean of day 1 to day 7.		
	Change from baseline each postbaseline timepoint		
Change from Baseline in Digestive sensations	Change from baseline in digestive sensations (abdominal pain, discomfort, bloating and distension) at end of treatment (as measured by AUC of hourly digestive sensations)	Baseline, Week 2 (Visit 6), Week 4 (Visit 8)	Continuous summary, 95% CI
Weekly averages change from baseline in Bristol Stool Form Scale (BSFS)	Baseline= mean (day -7 to day -1) Week 1= mean (day 1 to day 7) Week 2=mean (day 8 to day 14) Week 3=mean (day 15 to day 2) Week 4=mean (day 22 to day 28) Change from baseline	Baseline, Week 1, Week 2, Week 3, Week 4, Change from baseline at each postbaseline timepoint	Continuous summary, 95% CI

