4.3.1 Adverse Events

All adverse event reported during the study will be coded using MedDRA version 19.1. All summaries and listings will be presented of the safety population.

Table 15. AE classification

AE classification	Definition
Treatment Emergent Adverse Event (TEAE)	TEAE if: 
• Treatment Start date/time <= AE Start Date/Time <= Date of Last Treatment +1• And• PT not previously reported prior to Treatment• PT reported prior to Treatment however increased in severity after start of treatment
Serious Adverse Event (SAE)	Any event meeting the following criteria: 
• Results in death• Is life-threatening• Requires inpatient hospitalization or prolongation of an existing hospitalization• Results in persistent or significant disability or incapacity• Results in a congenital anomaly or birth defect 
These criteria will be identified by AE Serious criteria = Yes

Patients reporting multiple incidence of an adverse event mapping to the same PT will be counted only once overall, at the most severe severity level, and at the closest relationship to treatment. AEs will be summarized as described in [Table 6](#).

Table 16. Adverse Events

Summaries	Description	Summary Method
Overall Summary	
• TEAEs• Deaths• On-Therapy SAEs• Withdrawals Due to TEAEs (ADOs)	Categorical Summary
TEAEs	
• At Least One AE	
TEAEs By Severity	
• By SOC	
TEAEs By Relationship	
• By PT within SOC	
Listings of All Adverse Event for Patients with: 1. SAEs 2. ADOs 3. Fatal	For Patients meeting the defined criteria, list all all the patients Adverse Events	Data Listing – See Table Shell for variables to include

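### The protocol's BSFS recode removes the direction of a shift from hard to loose stool, the SAP does not say whether the recode applies, and neither document plans a diary summary of types 6–7

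*Protocol*

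**What the plan says.** Protocol 9.1.2 lists as a secondary assessment "Stool consistency (Bristol Stool Form Scale [BSFS]) with each BM", taken from the daily diary. The same diary asks about laxatives, suppositories and enemas.

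Protocol 11.3.3.3 then sets the scoring: "Daily diary BSFS scores will be recoded to represent discrepancies from a 'normal' stool type 4 as follows". Types 1 to 7 become 3, 2, 1, 0, 1, 2, 3. The section explains: "Hence a higher score represents greater discrepancy from a 'normal' stool consistency". Daily values average up to the first three stools, a day without a stool is missing, and daily values are averaged by week. Section 11.3.3.4 compares the weekly recoded averages between arms.

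SAP Table 14 defines the BSFS endpoint as weekly means and change from baseline, summarised descriptively with a 95% CI. It does not say whether the score is recoded or raw. SAP Section 5 lists changes from the protocol. For BSFS it corrects the time points and changes the model, and it then drops all formal modelling because the trial stopped at 20 randomised. It does not mention the recode.

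On harm, Protocol 3.2 reports of the Phase 3 IBS-C trials: "Diarrhoea was the most frequent TEAE and was reported in 3.0% of placebo-treated patients and 19.8% of linaclotide-treated patients". Exclusion criterion 1 (Protocol 6.3) treats BSFS 6 or 7 as loose or watery stool. SAP 4.3.1 tabulates TEAEs by system organ class and preferred term, by severity and by relationship. Neither document plans a count or proportion of BSFS 6–7 stools, days or participants.

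**The concern.** Linaclotide is expected to soften stools, and its leading known harm is softening them too far. A useful stool-form summary would separate three outcomes: still hard, corrected, and overshot. The recode merges the first and third. On that scale an arm that moves from hard to loose stool can look unchanged or slightly better, on a listed secondary endpoint.

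The SAP adds uncertainty, because two analysts following Table 14 could report different numbers from the same diaries.

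The diary holds stool-level information on this harm for both arms, but the SAP safety section does not draw on it. The by-arm picture of loose stools therefore depends on what is recorded as an adverse event, in a trial of 20 participants.

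**Working it through.** **Inputs.** The recode, the first-three-stools rule and the weekly averaging come from Protocol 11.3.3.3. The diarrhoea rates (19.8% and 3.0%) come from Protocol 3.2. The 20 randomised come from SAP 4.2. Ten per arm is an assumption based on 1:1 allocation.

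**1. Reproduce the recode.** |type − 4| for types 1 to 7 gives 3, 2, 1, 0, 1, 2, 3, which matches the protocol exactly.

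**2. Change score for each shift.** Recoded change = |to − 4| − |from − 4|. Raw change = to − from. On the recode, a negative change means closer to type 4.

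| Shift | Recoded change | Raw change |
|---|---|---|
| 2 to 4 (correction) | −2 | +2 |
| 2 to 6 | 0 | +4 |
| 1 to 7 | 0 | +6 |
| 3 to 5 | 0 | +2 |
| 1 to 6 | −1 | +5 |
| 2 to 7 | +1 | +5 |
| 3 to 6 | +1 | +3 |
| 3 to 7 | +2 | +4 |

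The recode hides some shifts into types 6–7 and registers others as worsening. The raw score keeps direction in every case.

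**3. Example weeks** (illustrative, one stool a day).

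| Week | Recoded mean | Raw mean | Days with type 6–7 |
|---|---|---|---|
| All type 2 | 2.0 | 2.0 | 0 |
| All type 4 | 0 | 4.0 | 0 |
| All type 6 | 2.0 | 6.0 | 7 |
| Two days type 7, four type 3, one type 2 | 12/7 = 1.71 | 28/7 = 4.0 | 2 |

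On the recode, a week of type 6 equals a week of type 2. On the raw scale those two weeks are clearly apart (6.0 against 2.0), but the mixed week with two watery days has the same mean as a week of type 4. On the recode the mixed week is 1.71, apparently better than 2.0.

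**4. First-three-stools rule.** A day of types 4, 4, 4, 6, 7, 7 is scored on the first three stools only. It gives 0 recoded or 4.0 raw, and the three loose stools are not counted.

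**5. What the adverse-event route can be expected to show.** With 10 per arm and the Phase 3 rates, expected participants with diarrhoea are 10 × 0.198 = 1.98 on linaclotide and 10 × 0.030 = 0.30 on placebo. The chance of none on linaclotide is (1 − 0.198)^10 = 0.802^10 = 0.11. The Phase 3 treatment periods were 12 and 26 weeks against 4 weeks here, so these rates are probably an upper bound.

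**The case against.** The BSFS score is an efficacy measure. Scoring distance from a normal stool gives the drug no credit for overshoot, which is a defensible choice for that purpose. Harm belongs in the safety tables, and diarrhoea is covered there: adverse events are reviewed at every visit from Visit 2 and at the follow-up call, may be spontaneous, observed by the investigator or elicited (Protocol 10.2), and are tabulated by preferred term, severity and relationship. On step 5's assumptions there is an 89% chance of at least one diarrhoea event on linaclotide.

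This argument stands to a large extent. It defeats four stronger readings that a reader might infer:

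- **That the weekly mean cannot show loose stool at all.** A sustained shift is plain on a raw scale, the summaries include minimum and maximum, and the recode itself gives +1 or +2 for several shifts.
- **That the SAP has switched to raw scoring, so that 2 to 6 is +4.** Table 14 does not say so, and Section 5 does not list the recode as dropped.
- **That diarrhoea would go unreported.** It would appear as a TEAE.
- **That a count of drug suspensions is already required by the note on delaying belt visits.** That note only moves visits. The capsule-count compliance in SAP 4.1.2.6 would also fall after a mid-treatment suspension, though it gives no reason.

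Two further cautions hold. Bisacodyl rescue is permitted during treatment (Protocol 7.6), so a bare count of loose days would mix rescue effects with drug effects. Repeated diary days are correlated within about ten people per arm and do not act as extra participants.

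The objection leaves a narrower gap. No rule links diary stool form to adverse-event recording, diary review at visits is described as a compliance check, and the planned BSFS summary either loses direction or can average away short episodes.

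**Conclusion.** The point holds in limited form. The protocol's recode loses direction: 2 to 6, 1 to 7 and 3 to 5 score 0, and 1 to 6 scores as an improvement of 1. The SAP leaves the scoring undefined, so the change for 2 to 6 is 0 or +4 depending on the reading. If the score is raw, sustained shifts show but short episodes may not. No summary of BSFS 6–7 is planned in either document, although the data are collected stool by stool.

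No planned conclusion is invalidated: the analysis is descriptive only, and diarrhoea remains in the adverse-event tables. The change is worth making because it settles an ambiguity and uses existing data on the drug's leading known harm.

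The verdict rests on the protocol and SAP alone. Table and listing specifications are in a separate document that was not available. The example weeks are illustrative, and 10 per arm is assumed.

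**What to change.** 1. State in SAP Table 14 whether BSFS is recoded or raw. If this departs from Protocol 11.3.3.3, list it in SAP Section 5.
2. Keep the weekly mean. If it is recoded, add a note that it does not separate hard from loose departures.
3. Add one descriptive table by arm for the Safety Population, using all recorded stools and not only the first three:
   - number and percentage of participants with at least one Treatment Period day with a BSFS 6–7 stool;
   - percentage of diary days with a recorded stool that include a BSFS 6–7 stool, at Baseline and Weeks 1 to 4, with a 95% CI for the arm difference. Compute the percentage per participant first, so that the interval reflects participants and not correlated days, and show the number of days with a stool.
4. Present that table overall and again excluding days on which the diary records laxative, suppository or enema use, and the day after.
5. Optionally, list participants whose study drug was suspended for diarrhoea, where this is recorded.

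None of this changes clinical management or needs new data collection. The cost is SAP wording and one more table, with wide intervals because only 20 were randomised. It may also show more loose stool on linaclotide than the adverse-event table alone.
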